11 APPROPRIATENESS OF MEASUREMENTS

11.1 Natural History Studies

Two ongoing prospective natural history studies of CLN2 disease (Weill Cornell Medical Center and University Medical Center, Hamburg, Germany) continue to provide evidence that rating scale scores change in a predictable manner with increasing disease duration (Steinfeld, 2002); (Worgall, 2007).

The Weill Cornell database comprises approximately 45 patients with genetically diagnosed CLN2 disease and includes Weill Cornell Scale scores, some Hamburg Scale scores, and MRI data, which have been shared with BioMarin (Crystal, 2004), Approximately half the patients have two assessments 2 weeks to 16 months apart.

The Hamburg registry includes both retrospective and prospective data from approximately 30 patients with CLN2 disease with scoring of 6-month periods from birth to 8-10 years of age. All participants are genetically diagnosed; data include Hamburg Scale scores, neurologic and cardiologic examinations, ophthalmology testing, routine clinical pathology, volumetric MRI, EEG, ECG, and echocardiogram. Although clinical data have accrued for up to 10 years, MRI data collection started in 2009 and these data have been shared with BioMarin ([name] and [name], Hamburg).

The Hamburg registry is a subset of Dem-CHILD, a multi-center clinical database of CLN disorders that currently has 72 CLN2 patients. This database continues to add sites and patients, collection of clinical and research information is ongoing.

The natural history data will be used to (1) better understand the properties of the CLN2 disease scale, (2) evaluate correlations between the scale and potential surrogate markers such as neuroimaging, (3) generate the comparison group that will be matched to the study population of this clinical study.

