14.2.1 Secondary Efficacy Analyses

Time to disease manifestation will be assessed for asymptomatic patients. For all patients, an analysis of interest is time to first confirmed decline, defined as 2 consecutive CLN2 assessments (i.e., approximately 4 weeks apart) with scores less than the baseline CLN2 score.

The time to first confirmed decline is defined by the earlier of the 2 CLN assessments.

The 0-to-9 point Hamburg CLN2 scores (incorporating the motor, language, and vision domains) and the total 0-to-12 point Hamburg CLN2 scores (motor, language, vision, and seizure), will be presented descriptively.

The following variables obtained by MRI of the brain will be presented descriptively:

- Volume of CSF
- Volume of cortical gray matter
- Volume of white matter
- Whole brain apparent diffusion coefficient

Endpoints may be compared to natural history data in untreated historical controls (data from a CLN2 disease patient registry and data from siblings with CLN2 disease, when available).

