3.2 Study Design

This is a Phase 2 open-label, multicenter study in pediatric patients < 18 years of age with CLN2 disease. The study is designed to assess disease progression in CLN2 patients treated with BMN 190 compared to natural history data from untreated historical controls (data from a CLN2 disease patient registry and data from siblings with CLN2 disease, when available). The comparison of treated subjects with untreated controls is from the time of the initiation of study drug.

The planned enrollment for this study is at least 10 subjects: at least 5 subjects with a Hamburg ML score \geq 5 points, at least 5 subjects with a ML score < 5 points, and at least 5 subjects < 2 years of age. Study eligibility and enrollment occur before (\leq 21 days) subjects are admitted to the hospital for surgical implantation of an ICV access device. The first infusion is administered at least 14 days from surgery to implant the ICV reservoir and no more than 28 days after surgery. The Baseline visit is to collect clinical scores and clinical laboratory parameters and is to be completed no more than 2 days before the first infusion.

BMN 190 are administered every 14 days from the date of the first infusion (\pm 3 days) for at least 144 weeks according to the subject's age. At study completion or early termination visit, subjects who have ICV device removal are required to have a device safety follow-up visit at 4 weeks (\pm 3 days) after ICV device removal. All subjects require a safety follow-up visit at 6 months (\pm 1 week) after last dose.

CLN2 assessments are scheduled every 4 weeks, study completion/early termination, and safety follow-up visits. Cranial MRI is assessed every 24 weeks and at study completion/early termination visit. Immunogenicity assessment is based on CSF and serum lab draws collected at baseline, every 12 weeks, study completion/early termination, and safety follow-up visits (serum only). PK assessment is based on CSF and serum lab draws every 24 weeks and at study completion/early termination visit.

	BMN 190-203 Statistical Analysis Plan, Version 2.0	Pg. 12 of 53
---	---	--------------

The safety and tolerability of treatment will be assessed by collection of adverse events, physical findings, vital signs, ECG, EEG, and clinical laboratory tests.

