4.6 Handling of Dropouts and Missing Data

Missing ML assessments for symptomatic patients (baseline ML < 6 points) will not have much impact on the assessment of the primary endpoint since the disease progression on ML score is close to linear, estimation of rate of decline in ML is reliable for follow-up periods of greater than 6 months and all subjects had been followed > 6 months. Impact of missing ML assessments for asymptomatic subjects (baseline ML = 6 points) is also expected to be low since the follow-up of matched Study 190-901 subjects is limited to the length of follow-up of the Study 190-203 subject matched. Additional analyses will be conducted as appropriate to evaluate the impact of the COVID-19 pandemic on the study conduct and results, especially for the treatment effect as estimated in the trial.

BIOMARIN®	BMN 190-203 Statistical Analysis Plan, Version 2.0	Pg. 17 of 53
------------------	---	--------------

Statistical models for time-to-event analyses accommodate variable follow-up arising from staggered accrual or early study discontinuation, using an assumption of missing at random.

The CLN2 assessment schedule for Study 190-901 is not regular and does not generally match CLN2 assessment frequency in Study 190-203. Summaries of CLN2 score over a window grid would have highly variable N which is difficult to interpret. For this reason, interpolation will be used. Summaries of matched Study 190-203 and Study 190-901 CLN2 data will be based on data that has been imputed to the Study 203 visit target, using linear interpolation between Study 190-901 subject visits. Details are provided in [Appendix 4](#).

Partial or missing dates for adverse events and medications will be imputed conservatively by assignment to the earliest and latest possible dates for start and stop dates, respectively.

Some patients only have year of birth recorded as permitted by the site Institutional Review Board. Age in integer months is provided at each visit for Denver assessment. For subjects with incomplete date of birth provided, the date of birth will be imputed by back-calculation of birth date from the date of Denver assessment: (date of Denver) – round ((age in months) x (365.25/12)). For subjects with multiple Denver assessments, the average of the imputed date of births is used.

BIOMARIN®	BMN 190-203 Statistical Analysis Plan, Version 2.0	Pg. 18 of 53
------------------	---	--------------

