13.1.3 Time to Unreversed 2-point Decline or Score of Zero

Response defined as the absence of an unreversed two-point decline or score of zero in ML score by last assessment relative to baseline, will be analyzed using Kaplan-Meier methods and the Cox proportional hazards model. An unreversed two-point decline is defined as any decline of 2 points or more that had not reverted to a 1-point decline (or better) as of the last recorded observation. An unreversed score of zero is a score of zero that did not subsequently increase to a score greater than zero as of the last recorded observation.

The Cox model will include an indicator variable for study group and no additional covariates since the study groups are matched on the important variables. Kaplan-Meier curves will be produced for the two matched cohorts. Time from baseline to the first unreversed 1-point decline in ML score will also be displayed by Kaplan-Meier method. The Cox model and Kaplan-Meier curves will weight Study 190-901 subjects according to the number of matches: weights 1/3, 1/2, 1 normalized to the number of Study 190-901 subjects matched to Study 190-203 subjects, for 3, 2, 1 matches, respectively.

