13.2 Secondary Efficacy Endpoint(s)

13.2.1 Time to Disease Manifestation

For analysis purposes, asymptomatic patients are defined as the patients with baseline MLVS = 12. Subsequent disease manifestation is defined as post-baseline consecutive measurements of M, L, V, or S scores that are less than 3 and at least 22 days apart. The time of disease manifestation is defined as the time of the first of the two measurements demonstrating the deficit. Kaplan-Meir analysis will be performed.

For patients who have not presented with CLN2 disease symptoms prior to initiation of treatment (baseline), onset of disease symptoms captured in AE reporting will be described.

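### Time-to-decline analyses set 4-weekly ratings against irregular control ratings, with no event-date rule and no allowance for interval censoring, so the control curve would probably sit late

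*SAP*

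**What the plan says.** SAP 13.1.3 takes time to an unreversed 2-point ML decline or score of zero, which "will be analyzed using Kaplan-Meier methods and the Cox proportional hazards model". The Cox model has a study-group indicator and no other covariate. The same section adds a 1-point version: "Time from baseline to the first unreversed 1-point decline in ML score will also be displayed by Kaplan-Meier method". Section 13.1.4 handles time to an unreversed zero in the same way, and 13.1.6 plans time-to-event analyses for the separate motor and language scales.

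On rating frequency, SAP 3.2 says "CLN2 assessments are scheduled every 4 weeks" for treated children. For controls, SAP 4.6 says "The CLN2 assessment schedule for Study 190-901 is not regular and does not generally match CLN2 assessment frequency in Study 190-203". Its remedy, linear interpolation, is written for summaries of scores over time (4.6, 13.1.5, Appendix 4). For time-to-event models, 4.6 speaks only of variable follow-up under a missing-at-random assumption.

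Section 13.1.3 gives no event date. Two neighbouring endpoints do have a rule. For disease manifestation (SAP 13.2.1), "The time of disease manifestation is defined as the time of the first of the two measurements demonstrating the deficit". For confirmed decline (Protocol 14.2.1), "The time to first confirmed decline is defined by the earlier of the 2 CLN assessments".

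**The concern.** A decline in ML score happens at an unknown time between two ratings. Ordinary Kaplan-Meier and Cox methods need one date per event, and the usual choice is the first rating that shows it. With 4-weekly ratings that date is at most about 4 weeks late. With sparse ratings it can be late by a whole gap. Here the sparse ratings are all on the control side, so the comparison mixes the drug effect with a difference in how quickly a decline is detected.

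At stake are the control median, the separation of the curves, and the hazard ratio. In the prior study (Protocol 7.2), time to a 2-point decline was the primary outcome and the 345-day control median was a central result. In this study the same type of analysis supports the primary comparison of rates of decline.

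**Working it through.** The documents give no hazard ratio, event count or power for this analysis, so there is no planned figure to reproduce. The size was found by formula and simulation.

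**Inputs from the documents**
- Treated rating gap: 28 days (SAP 3.2).
- Control rating gap: not given. The nearest indication is the Hamburg registry, a subset of DEM-CHILD, "with scoring of 6-month periods from birth to 8-10 years of age" (Protocol 11.1). Assumed mean gap 182 days, range 91 to 365, each gap varying uniformly by 50% either way.
- Prior study (Protocol 7.2): control median 345 days; decline per 48 weeks 2.12 (SD 0.98) in controls and 0.27 (SD 0.35) in treated children.
- Numbers: 14 treated children and up to 14 × 3 = 42 controls (SAP Appendix 3). Full 3-1 matching makes the normalised weights equal, so weights were not modelled.
- Follow-up: 144 weeks, to Day 1009.

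**Step 1: dating delay.** For gaps with mean g and coefficient of variation c, the mean delay to the next rating is (g/2)(1 + c²).
- Treated, fixed 28 days: 28/2 = 14 days.
- Controls, c² = 1/12: 91 days gives 49; 182 gives 91 × 13/12 = 99; 365 gives 198.
- Simulated with exponential event times: 51, 104 and 217 days, slightly longer because under a constant hazard events fall nearer the start of a gap.

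**Step 2: control median.**
- Exponential event times, true median 345 days: 364 if rated every 28 days, and about 395, 447 and 530 at gaps of 91, 182 and 365 days. At 182 days the shift against 4-weekly rating is 447 − 364 = 83 days.
- Linear decline, child starting exactly at the rated integer: 336 × 2/2.12 = 317 days, seen at the next 4-weekly visit, day 336. With gaps averaging about 6 months it appears at 385 to 452 days, depending on how the gaps vary. Shift: 49 to 116 days.
- Linear decline, child starting up to one point below the rated integer (1.5 points left to lose on average): 336 × 1.5/2.12 = 238 days, seen at day 252. With gaps averaging about 6 months: 349 to 361 days. Shift: 97 to 109 days.

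The absolute median depends on where the child starts within an integer score. The shift is always late, by 49 to 116 days, or roughly 2 to 4 months.

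**Step 3: hazard ratio, treated v control** (20,000 per group; treated rated every 28 days)

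| True HR | Controls also 28 days | 91 days | 182 days | 365 days |
|---|---|---|---|---|
| 1.0 | 1.00 | 1.06 | 1.15 | 1.37 |
| 0.5 | 0.50 | 0.52 | 0.55 | 0.61 |
| 0.25 | 0.25 | 0.26 | 0.26 | 0.28 |
| 0.1 | 0.10 | 0.10 | 0.10 | 0.09 |

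With the prior study's linear decline rates and starts at the integer, the hazard ratio is 0.041 with exact dates and 0.037, 0.035 and 0.033 at the three sparse gaps.

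**Step 4: no true effect, 14 v 42, 1,500 runs, two-sided 5% Wald test.** False findings against the drug: 2.5% with equal 28-day ratings, 10% at 182 days, 24% at 365 days. False findings for the drug: 1.0%, 0.3% and 0.4%.

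**Step 5: does the remedy work?** An interval-censored exponential likelihood returned 0.99 to 1.00, 0.50, 0.25 and 0.10 for the four true values at every gap. The data were generated from that same model, so this is a favourable test. Thinning treated ratings to one control schedule at 182 days gave 0.99, 0.51, 0.26 and 0.10.

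A small opposite effect: SAP 4.3 counts control time in 30-day months, so an event at 345 days is recorded at 345 × 30/30.44 = 340, 5 days early.

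**The case against.** **No dating rule is written.** A reader might infer that the SAP dates these events at the first rating. Section 13.1.3 does not say so; the written rules belong to other endpoints. This stands. First-rating dating is the likely reading, and the missing rule is itself a gap.

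**The SAP did not correct this bias in one place and forget it in another.** SAP 4.6 interpolates because windowed summaries would rest on changing numbers of children. It does not mention detection delay. This stands.

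**Control spacing is unknown.** The 6-month figure is a scoring period in a subset of about 30 patients whose data are partly retrospective. Retrospective scores may carry better dates, and nothing supports year-long gaps as typical. This stands, so the size is conditional.

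**A reader might infer that the hazard ratio is materially distorted, or that the curve and hazard ratio are always biased in opposite directions.** The results do not support either as a general statement. For a nil or modest effect both lean against the drug. Only at the prior study's very large effect does the hazard ratio lean slightly towards the drug. In the model with starts below the integer it moves from 0.075 to 0.069, or ln(0.075/0.069) = 0.083. Against a standard error near 0.61 for 14 v 42 (about 3.7 treated events), that is about one-seventh of a standard error.

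**The simulation is simplified.** It omits the reversal rule and does not model baseline ML 6 separately. This limits precision but does not remove the delay.

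**Conclusion.** The concern holds in a limited form. As written, 13.1.3, 13.1.4 and 13.1.6 do not define the event date or allow for interval censoring, although the two groups are rated at different frequencies.

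If events are dated at the first rating that shows them, and control gaps average about 6 months, the control median is late by roughly 2 to 4 months. The difference in medians, or the separation of the curves if the treated median is not reached, is understated. The hazard ratio is biased against the drug for a nil or modest effect. At the effect seen before it changes little, and the conclusion would not change.

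A reader should not infer that the plan inflates the apparent benefit. The primary t-test compares slopes between a starting and an ending rating and does not use these event dates.

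**What to change.** In SAP 13.1.3, carried to 13.1.4 and 13.1.6:

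1. State the date on which an unreversed decline or score of zero counts as an event.
2. Report the distribution of Study 190-901 rating gaps in the matched set.
3. Add a sensitivity analysis with event time interval-censored between the last rating without and the first rating with the unreversed decline. Use a Turnbull curve with the existing match weights, and an interval-censored proportional hazards or parametric model.

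An alternative to item 3 is to thin each treated child's ratings to the visit times of one matched control at a time, then average over that child's one to three controls. The averaging must be specified, because the controls in a set have different schedules.

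Cost: SAP wording and programming on existing data. The curves would be stepwise and defined only up to intervals. With few treated events the interval-censored hazard ratio may be unstable, so it should sit beside the planned analysis.

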13.1.4 Time to Unreversed Score of Zero

Time to an unreversed ML score of zero will be analyzed similarly as time to unreversed ML 2-point decline or score of zero.

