- If two subjects experience the same NCI CTCAE v. 4.0 Grade 3 AE, or if one subject has a Grade 4 AE that, in the investigator's opinion, is not related to the underlying disease, the BioMarin medical monitor will consult the DRB to evaluate the risk/benefit of continuing the study.

Another possible AE is infection from or failure of the indwelling ICV catheter. If an infection is suspected, blood and CSF samples will be drawn for assessment. The subsequent course of therapy, which is guided by site neurosurgical standards of care, may include antibiotic therapy, catheter reposition, or catheter withdrawal. If BMN 190 treatment is suspended, BMN 190 may resume if no more than 4 consecutive missed doses elapse after the last given dose.

If BMN 190 treatment is suspended for any reason, study participation may resume if no more than 4 consecutive doses were missed from the prior given dose.

If two or more subjects experience unacceptable drug-related toxicity, BioMarin may suspend further enrollment in the study pending a review of the data and upon consultation with the DRB. Depending on the nature and severity of the unacceptable drug-related toxicity, dosing of subjects already enrolled in the study may be continued or suspended pending further review. BioMarin will consult the DRB to aid in evaluating the risks of continuing the study and options for modification of the study to minimize subject risk.

Subjects who have a loss of 3 or more points on the combined motor and language components of the Hamburg CLN2 rating scale in any 1 year period may be discontinued at the discretion of the Investigator.

Subjects with a score of 0 on the combined motor and language components of the Hamburg CLN2 rating scale at two consecutive visits will be discontinued from treatment.

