Appendix 3: Matching of Study 190-901 and Study 190-203 Subjects

The population for the primary analysis is based on the ITT population and a 3-1 matching algorithm. This matching algorithm is based on maximizing the number of Study 190-203 subjects matched to Study 190-901 subjects and satisfying several criteria (baseline ML score equal, genome: equal number of common alleles, baseline age close and no more than 3 months apart). The data of Study 190-901 subjects will be restricted and includes the assessment at the age of the match as the baseline assessment. Duration of follow-up is measured with respect to this baseline. Follow-up assessments up to the largest duration that is less than or equal to the full follow-up duration of the matched 190-203 subject are included for the matched analysis. If this derived duration of follow-up for the Study 190-901 subject is not of duration 6 months or greater, then matching at this age of assessment will not be considered. For Study 190-901, where the first assessment of ML has the value 6, backwards imputation of the value 6 to earlier ages is allowed.

Distance is defined as the absolute value of the difference in baseline age for the potential match. Study 190-203 subjects are paired off from first through last and there are potentially 14 matched pairs. No Study 190-901 subject is matched more than once. To maximize the number of matched pairs, and overall low mean squared distance, at each pairing:

- Identify the Study 190-203 subject who has not yet been matched and has the least potential Study 190-901 candidates for pairing based on the requirement for equal baseline ML score, equal number of common alleles and distance ≤ 3 . If greater than one Study 190-203 subject is identified, break the tie by considering the number of potential Study 190-901 candidates for matching based on the requirement of distance ≤ 2 . Potentially, there are still ties and repeat as needed using distance criteria based on thresholds ≤ 1 and ≤ 0 .

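### Time to ML zero: treated children discontinued after a 3-point loss in a year are censored as missing at random, although their own fast decline caused the exit

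*SAP*

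**What the plan says.** **Stopping rule.** Protocol 9.3.3.1 has two rules based on the ML score. The first is optional: "Subjects who have a loss of 3 or more points on the combined motor and language" components of the scale, within one year, "rating scale in any 1 year period may be discontinued at the discretion of the Investigator". It does not say whether the child is discontinued from treatment or from the study. The second is mandatory and names treatment: a child with a score of 0 on the "rating scale at two consecutive visits will be discontinued from treatment". The second rule acts after the zero endpoint has occurred. The first can act before it.

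**Analysis.** SAP 13.1.4, added in version 2.0, says: "Time to an unreversed ML score of zero will be analyzed similarly as time to unreversed ML 2-point decline or score of zero". The method it points to is in SAP 13.1.3: Kaplan-Meier curves and Cox regression, where "The Cox model will include an indicator variable for study group and no additional covariates". SAP 4.6 says that time-to-event models accommodate "early study discontinuation, using an assumption of missing at random". The sensitivity analyses in SAP 13.1.2 concern the rate of decline. None addresses this censoring.

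**Controls.** SAP 4.6 says "the follow-up of matched Study 190-901 subjects is limited to the length of follow-up of the Study 190-203 subject matched", and Appendix 3 gives the same restriction in detail.

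**Ratings after stopping.** Protocol 9.3.3 says that children who stop treatment should be encouraged to continue assessments. Table 9.1.1 schedules CLN2 ratings at the Early Termination, Device Safety and 6-month Safety visits.

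**The concern.** Censoring is harmless only if censored children have, given what the model conditions on, the same future risk as those who remain. Here the exit is triggered by the outcome scale itself. A child who has just lost 3 points in a year and stands at ML 1, 2 or 3 is closer to zero, and moving faster, than the average child still at risk. The Cox model conditions on study group alone, so it cannot account for the ML history that led to the exit. Registry controls have no such rule.

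At stake are the time-to-zero curve and its hazard ratio. A drug with no effect could show fewer treated children reaching zero. The problem is largely confined to this analysis: a 3-point loss is already a decline of at least 2 points, so it counts as an event in SAP 13.1.3 unless later reversed.

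**Working it through.** The plan states no event count or power for this endpoint (SAP 3.5 says power was not considered), so there is no figure of its own to reproduce.

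**Inputs from the documents.**
- ML decline per 48 weeks in the earlier study, mean (SD): 0.27 (0.35) treated, 2.12 (0.98) historical controls (Protocol 7.2). As a check, 2.12 − 0.27 = 1.85, the stated difference.
- Entry ML 3 to 6; treated children rated every 4 weeks to week 144, with a final rating at week 168.
- Potentially 14 matched treated children, up to 3 controls each (SAP Appendix 3).

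**Step 1: how many children would trigger the rule?** Three points per 52 weeks is 3 × 48/52 = 2.77 per 48 weeks.
- At the natural-history rate: (2.77 − 2.12)/0.98 = 0.66, upper tail 25%, so 14 × 0.254 = 3.6 children.
- Whole-point scoring makes the trigger easier to meet, because three successive one-point drops span only two intervals. A latent rate of 2 × 48/52 = 1.85 can then suffice: (1.85 − 2.12)/0.98 = −0.28, upper tail 61%. The simulation below gives about 60%.
- At the earlier treated rate: (2.77 − 0.27)/0.35 = 7.1, a probability of about 5 × 10⁻¹³, effectively none.

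**Step 2: how many would leave before zero?** A child entering at ML 3 who loses 3 points is at zero and counts as an event. In the simulation 15% of treated children are already at zero when they trigger, which leaves 60% − 15% = 45% who could leave above zero.

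**Step 3: effect on the hazard ratio when the drug does nothing.** Both groups decline at 2.12 (0.98). Assumptions not in the documents: baseline ML uniform on 3 to 6, linear latent decline scored in whole points, controls rated every 4 or every 26 weeks. Each treated child has three controls, so the normalised weights all equal 1. Controls are cut to the matched child's follow-up unless stated.

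| Scenario | Controls every 4 weeks | Controls every 26 weeks |
|---|---|---|
| No discontinuation | 0.98 | 1.23 |
| Half of triggered children leave unrated | 0.78 | 0.96 |
| All leave unrated | 0.57 | 0.66 |
| All leave unrated, controls not cut | 0.61 | 0.70 |
| All leave, 6-month rating captured | 0.73 | 0.86 |

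A second simulation of the 4-weekly case gave about 0.50 (all leave) and 0.82 (half leave), hence the ranges of about 0.5 to 0.6 and about 0.8.

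With 4-weekly controls and all leaving, treated events fall from 84% to 39%. Control events also fall, from 84% to 50%, because their follow-up is cut.

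The relative shift is similar on both rating schedules. Half leaving: 0.78/0.98 = 0.80 and 0.96/1.23 = 0.78. All leaving: 0.57/0.98 = 0.58 and 0.66/1.23 = 0.54.

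**Step 4: candidate remedies, same no-effect setting.**
- Counting every child who leaves under the rule as an event gives 1.13 (half leave) or 1.41 (all leave) with 4-weekly controls, and 1.44 or 1.60 with 26-weekly controls. This overcorrects.
- A composite of zero or a 3-point loss within a year, defined alike in both groups, gives about 0.94 to 1.00 when rating schedules match.

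**The case against.** A reader might infer that the fastest treated decliners cannot become events while untreated controls can. The documents do not support that, for four reasons.

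- **The rule is discretionary**, and a child entering at ML 3 who triggers it has already had the event.
- **Later ratings are scheduled.** SAP 3.2 says all subjects require the 6-month visit, and capturing that rating moves the all-leave hazard ratio from 0.57 to 0.73. This mitigation is incomplete. The Early Termination visit falls within 3 days, so it would largely repeat the triggering score. Protocol 12.11 and 12.12 drop the later visits when BMN 190 continues elsewhere, and continued assessment is only encouraged.
- **Controls are cut too.** Appendix 3 keeps only "Follow-up assessments up to the largest duration that is less than or equal to the full follow-up duration of the matched 190-203 subject". This removes control events but not the bias (0.57 with the cut, 0.61 without), because a control's cut-off does not depend on that control's own decline.
- **Sparse control ratings push the other way.** SAP 4.6 calls the registry schedule irregular, and Protocol 11.1 describes the Hamburg registry as scored in 6-month periods. With 26-weekly controls the half-leave case is close to 1. That is two errors offsetting each other, not validity.

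The size also rests on assumptions. The 2.12-point rate comes from controls for a study that enrolled children aged 3 or older, whereas this study plans at least 5 children under 2. The discontinuation probabilities are assumed.

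Finally, this is one supportive analysis. A fast decliner still counts against the drug in the primary slope and, unless reversed, in the 1- and 2-point analyses. Reasons for discontinuation are already to be summarised (SAP Section 6), although not specifically for this rule.

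**Conclusion.** The concern holds as a limited one. A treated child who leaves under the 3-point rule above ML 0 with no later rating is informatively censored in the time-to-zero analysis. A group-only model under missing at random does not address this, and the resulting bias favours BMN 190.

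With no drug effect and 4-weekly controls, the hazard ratio is about 0.5 to 0.6 if all triggered children leave unrated and about 0.8 if half do; the correct value is 1.0. Less frequent control ratings offset part of this. At the earlier study's treated decline rate almost nobody triggers the rule, so the risk is mainly to the validity of the comparison if the drug works poorly.

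A reader might go further and infer that the reported curve must favour treatment. That would need the number of children discontinued this way, which the documents do not give. If there were none, the point is settled by saying so. The primary slope analysis is not challenged, and the 2-point analysis is largely unaffected.

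**What to change.** In SAP 13.1.4:

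1. Use every CLN2 rating after discontinuation, including the Early Termination, Device Safety and 6-month visits. Report how many children were discontinued after a 3-point loss without reaching zero.
2. Beside the planned zero-only analysis, report a composite: first unreversed ML of zero, or loss of 3 or more ML points within any 1-year period, defined identically for treated children and matched controls. Note that irregular registry ratings delay detection in controls.
3. Add one sensitivity analysis that counts children discontinued under this rule with no later rating as events. Label it a conservative bound, because it is biased against treatment, and do not make it the main rule.

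In Protocol 9.3.3.1, reconcile the 3-point sentence with the score-of-zero sentence so that it states whether discontinuation is from treatment or from the study. The stopping rule itself is not challenged.

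The cost is a few lines of text and one or two extra supportive runs on data already collected. The composite partly overlaps the 2-point endpoint.
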